12.1.3 Causal Assessment

The following “binary” decision choice will be used by the investigator to describe the causality assessment:

- Reasonable possibility of relatedness
- No reasonable possibility of relatedness

The term “reasonable possibility of relatedness” is meant to convey, in general, that there is enough evidence or argument to suggest a causal relationship. The investigator should consider the following, before reaching a decision on causality assessment:

- Time relationship between study drug intake and event’s onset
- Dechallenge
- Rechallenge
- Medical history
- Study treatment
- Mechanism of action of study drug
- Class effect
- Concomitant treatments in use

- Withdrawal of study treatment
- Lack of efficacy/worsening of existing condition
- Erroneous treatment with study medication or concomitant medication
- Protocol-related process

Action taken with study drug due to the AE:

- None
- Drug permanently discontinued
- Drug temporarily discontinued
- Unknown/not applicable

Other action taken:

- Specific therapy/medication
- Surgical medical procedure
- (Prolonged) hospitalisation

Outcome:

Each single AE must be rated by choosing 1 of the following:

- Recovered/resolved
- Recovering/resolving
- Not recovered/not resolved
- Recovered with sequelae/resolved with sequelae
- Fatal
- Unknown.

12.1.4 Abnormal Laboratory Values/Vital Signs/Electrocardiograms

Laboratory/vital signs/ECG abnormalities should be reported as AE/SAEs if any 1 of the following criteria is met:

1. The result is clinically significant or associated with signs/symptoms
2. Requires additional diagnostic testing and/or interventions
3. Leads to a change in dose, discontinuation or interruption of the study drug.

Results of an abnormal test results without any of the above criteria do not constitute an AE. Any test result determined to be an error is not required to be reported as an AE. A repeat measurement is in that situation may be recommended.

12.1.5 Overdose

A drug overdose is defined as the accidental or intentional use of a drug or medicine or an administration error in drug administration above 20mg as single dose or 2 or more doses

above 5mg/dose. Every overdose must be reported to ICON Pharmacovigilance and Safety Services within 24 hours of awareness, irrespective of whether the overdose was associated with an AE/SAE.

12.1.6 Partner Pregnancies

Pregnancy outcomes must be collected for the female partners of the subjects who took study treatment in this study. Pregnancy itself is not regarded as an AE unless there is suspicion that the study drug may have interfered with the effectiveness of a contraceptive medication. If a pregnancy is reported for a subject's partner, study drug will be immediately discontinued. The outcome of all pregnancies (spontaneous miscarriage, elective termination, normal birth or congenital abnormality) must be followed up and documented. Follow up should be performed up to delivery and examination of the new-born, after which a follow-up report should be sent with any new information regarding the pregnancy and the outcome of the birth. After study drug discontinuation, the subject should continue with all study schedule assessments, except study drug administration. The male study subject has to continue to wear a condom for at least 3 months after the last medication intake. Unprotected intercourse with his pregnant partner presents a risk of toxicity to the unborn child.

All congenital abnormalities/birth defects should be classified as SAEs. Spontaneous miscarriages should also be reported and handled as SAEs. Elective abortions without complications should not be handled as SAEs, but should be reported as AEs.

Pregnancies must be reported to ICON Pharmacovigilance and Safety Services using the reporting details and timelines provided in [Section 12.1.8](#) within 24 hours of awareness.

12.1.7 Adverse Events of Special Interest

Some AEs, despite their severity or outcome, will be expedited due to the relevance for subject safety or study drug safety profile. These AESIs should be reported as expedited within 24 hours of awareness to ICON Pharmacovigilance and Safety Services:

1. Cardiovascular event (acute myocardial infarction, brain stroke, transient ischemic attack, unstable angina, congestive heart failure)
2. Prostate cancer
3. Lower extremity oedema \geq Grade 3 (which is not due to local pressure /venostasis effects such as may be caused by socks or other clothing).
4. Polycythaemia as measured by a haematocrit $> 54\%$
5. Fragility fracture
6. Development of sleep apnoea
7. Development of osteoporosis as per DEXA measurement (T score ≤ -2.5)
8. Breast cancer.

12.1.8 Reporting of Serious Adverse Events and Adverse Events of Special Interest

Investigators and other site personnel must inform ICON Pharmacovigilance and Safety Services of any SAE/AESI that occurs during the course of the study whether or not considered causally related to the investigational product or to the study procedure(s): SAE from the time of informed consent until the 90 days after last dose of study drug, AESI from the time of randomisation until 90 days after last dose of study drug and within 24 hours of when he or she becomes aware of it.

Follow-up information on SAEs/AESIs must also be reported by the investigator within the same time frames.

If a non-serious AE becomes serious, this and other relevant follow-up information must also be provided to ICON within 24 hours as described above.

All SAEs/AESIs will also be recorded in the eCRF. The investigator is responsible for informing the Ethics Committee of the SAE/AESI as per local requirements.

Paper SAE/AESI forms should be completed at the site and faxed/mailed to the relevant ICON Pharmacovigilance and Safety Services or e-mailed to the global email distribution list within 24 hrs of awareness of the event.

SAE/AESI reports should be sent to:

[REDACTED]

If the report is sent via email, then the completed and signed SAE/AESI or Pregnancy report form must be attached to the email. A notification email of the event describing it in the email text is not sufficient.

Alternatively, the following fax number can be used for completed SAE/AESI reporting forms.

[REDACTED]

There may be situations when an SAE/AESI has occurred and the investigator has minimal information to include in the initial SAE/AESI report. However, it is very important that the investigator always makes an assessment of causality for every event prior to transmission of the SAE/AESI report form. Minimum criteria are identifiable subject (number), a suspect product (i.e., study drug or concomitant medication), an identifiable reporting source (investigator/study site identification), and an event or outcome that can be identified as serious or as an AESI. The investigator may change his/her opinion of causality in the light of follow-up information, amending the SAE/AESI report form accordingly. The causality assessment is one of the criteria used when determining regulatory reporting requirements for SAEs.

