During the 24 week treatment period, subjects will take the required dose weekly (\pm 1 day from the time schedule of regular planned dose), starting with the first dose being taken at the baseline visit. The treatment period will consist of up to 24 weekly doses of BGS649. The capsule will be taken orally by the subject with water. Subjects receiving active doses of BGS649 in Study MBGS205 will continue with the same dose in Study MBGS206; this transfer will be handled by the interactive response technology (IRT) and the blind will be

maintained. Subjects receiving placebo in Study MBGS205 will be re-randomised, using IRT, on a 1:1:1 basis to each of the active treatment arms:

- BGS649 [REDACTED] capsules)
- BGS649 [REDACTED]
- BGS649 [REDACTED].

If one or more dosing arms are dropped during the conduct of Study MBGS205 these will not be progressed in Study MBGS206 and subjects switching from placebo will be randomly allocated to available dose arms.

Details of the safety assessments to be performed are provided in [Section 12](#).

[figure not shown]
The safety of the study will also be periodically monitored through a data monitoring committee (DMC) and will include relevant subject data from Study MBGS205 and Study MBGS206.

To ensure adequate safety monitoring, serum total testosterone levels will be evaluated at each visit by an independent unblinded physician (see [Section 9.3.4](#) and [Section 16.3](#)), and if a subject meets the discontinuation criteria (total testosterone ≥ 1500 ng/dL [52 nmol/L] at any 2 consecutive time points throughout both studies the subject will be discontinued from the treatment. This would also include situation when first testosterone value that meets this threshold of ≥ 1500 ng/dL [52 nmol/L] was measured during MBGS205 and consecutive testosterone during study MBGS206.

Details of the efficacy assessments to be performed are provided in [Section 11](#).

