- 2 Only subjects receiving placebo in Study MBGS205 to be randomised. Subjects already on active in Study MBGS205 will maintain their treatment allocation
- 3 All blood samples are to be collected after 8 hours fasting, after ECG and vital sign measurements have been performed
- 4 A microscopic examination including RBC and WBC or urinary protein will be performed only when dipstick evaluation is positive for WBC and/or blood or protein
- 5 Bone turnover markers include CTx1, osteocalcin, bone alkaline phosphatase, and PINP
- 6 Has to be collected before 11 am. If the sample was inadvertently taken after this time, a retest is allowed after a discussion with the Medical Monitor.
- 7 All subjects that are not vasectomised will be asked to provide a semen sample. Subjects that provided semen sample for PK will also have plasma for PK drawn at the assessment visit Semen sample collection is not required to be the same day as the assessment visit. Therefore, semen PK collection is allowed ± 48 hours around the plasma PK attendance visits.
- 8 Subjects should come well hydrated, drinking water the night before and the morning before the impedance measurements
- 9 Activity wrist monitors will be collected from subjects at EOT visit of the Study MBGS205. If the activity wrist monitor was not performed before EOT of Study MBGS205 and collected at EOT Study MBGS205, it can be applied at the Baseline visit of current study and worn for 7 c consecutive days and collected at Visit 2. An activity wrist monitor will also be worn for 7 continuous days after Visit 7 (EOT) and collected at Visit 8 (FU)
- 10 Some questionnaires will be new for some subjects and completed first time at the Baseline visit
- 11 For subjects that discontinued early, EOT DEXA scan will be performed only if they reached minimum Week 36 (Visit 4) active treatment period. In order to accommodate scheduling, EOT DEXA can be performed within 5 days before the EOT visit or 5 days after the EOT Visit
- 12 [REDACTED]
- 13 AEs, SAEs, and AESIs collected from signature of informed consent

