4. Total testosterone \geq 1500 ng/dL (52 nmol/L) at any 2 consecutive scheduled visits during and in between the both studies MBGS205 and MBGS206. This would also include situation when first testosterone value that meets this threshold of \geq 1500 ng/dL

[52 nmol/L] was measured during MBGS205 and consecutive testosterone during Study MBGS206.

5. Liver laboratory values of:

- ALT or AST > 5 times the ULN

If the increase in ALT or AST is associated with normal bilirubin and ALP, the medical evaluation of withdrawing a subject can be made on a repeat AST/ALT test taken within 48 hours. (Repeated parameters should include: ALT, AST, alkaline phosphatase and total bilirubin). The subject should interrupt study drug until the repeat liver enzymes are available. If repeat liver parameters are all within the normal range, dosing may be continued. If not normalised the subject should be permanently discontinued.

or

- ALT or AST > 3 times the ULN and bilirubin total > 2 times ULN or International Normalised Ratio (INR) > 1.5 or the appearance of worsening fatigue, nausea, vomiting, right upper quadrant pain/tenderness, fever, rash, or eosinophilia
- A hepatic event leading to subject discontinuation should be followed up until event resolution, or becomes not clinically significant

6. Any of the following laboratory abnormalities:

- Renal function values that require discontinuation:
 - Discontinue investigational treatment for a subject if individual serum creatinine increases $\geq 50\%$ compared to Baseline (and is considered clinically significant), or in the event of treatment emergent proteinuria (albumin: creatinine ratio > 300 mg/g or > 30 mg/mmol; protein: creatinine ratio ≥ 500 mg/g or > 50 mg/mmol) (Creatinine can be repeated once within 7 days of initial alert. Study drug administration should be suspended during this time and resumed only if repeat creatinine is back to pre-alert level)
 - A renal event leading to subject discontinuation should be followed up until event resolution (serum creatinine within 10% of Baseline, protein-creatinine ratio within 50% of Baseline), stabilises or becomes not clinically significant, or is assessed as being chronic

7. Subject missed 4 or more consecutive study drug dosing

8. Development of prostate cancer or PSA increase more than 1.4 ng/mL above Baseline level in study MBGS205. It is recommended that in these cases subjects undergo urologic consultation

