12.1.2 Recording of Adverse Events

For the purposes of this study, any detrimental change in the subject's condition, after signing the ICF and any unresolved AEs from MBGS205 up to 90 days after the last administration of study drug should be considered an AE.

The following variables will be recorded for each AE: verbatim/AE description and date for AE start and stop, severity, seriousness, causality rating, whether or not the AE caused the subject to discontinue, and the outcome. If the severity of the AE changes, a new AE must be recorded.

SAEs and AEs will be recorded after signing of the informed consent. All AEs/SAEs have to be reported, whether or not considered causally related to the investigational product or to the study procedure(s).

All ongoing AEs/SAEs should be followed up until resolution or stabilisation or the last visit if in the investigator's opinion, the AE is unlikely to resolve due to the subject's underlying disease.

At any time after the FU visit, if an investigator learns of an SAE that can be reasonably related to study drug, he/she should promptly notify the sponsor.

Intensity

The investigator will assess the intensity of AEs based on the following definitions:

1. Mild (awareness of sign or symptom, but easily tolerated)
2. Moderate (discomfort sufficient to cause interference with normal activities)
3. Severe (incapacitating, with inability to perform normal activities).

It is important to distinguish between serious and severe AEs. Severity is a measure of intensity whereas seriousness is defined by the criteria in [Section 12.1.8](#).

An AE of severe intensity need not necessarily be considered serious. For example, nausea that persists for several hours may be considered severe nausea, but not an SAE. On the other hand, a stroke that results in only a limited degree of disability may be considered a mild stroke but would be an SAE.

For an AE to be a suspected drug-related event there should be at least a reasonable possibility of a causal relationship between the study drug and the AE.

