13.4.2 Secondary Endpoints

13.4.2.1 Secondary Safety Endpoints

1. In subjects that were randomised to active treatment in Study MBGS205 by dose group:
 - Percentage change in hip bone mineral density measured by DEXA (g/cm^2) from Baseline in Study MBGS205 to Week 48 in Study MBGS206
 - Percentage change in bone turnover markers (C-terminal telopeptide [CTx1], osteocalcin, bone alkaline phosphatase, and procollagen type 1 N-propeptide [P1NP]) from Baseline in Study MBGS205 to Week 48 in Study MBGS206
 - Proportion of subjects with T-scores ≤ -2.5 at Week 48
 - Percentage change in bone density and bone biomarkers adjusted for vitamin D deficiency from Baseline in Study MBGS205 to Week 48 in Study MBGS206
 - Change of oestradiol (absolute and percentage) to Week 48
 - Proportion of subjects that overshoot testosterone (total testosterone above 1000 ng/dl [35 nmol/L], from first dose of study drug in Study MBGS205 until study completion)
 - Change in PSA from Baseline in Study MBGS205 to Week 48 in Study MBGS206
 - Change in haematocrit from Baseline in Study MBGS205 to Week 48 in Study MBGS206
 - Change in blood pressure (systolic and diastolic) Baseline in Study MBGS205 to Week 48 in Study MBGS206
 - Treatment emerged AE, SAE, and AESI (from first dose of study drug in Study MBGS205 until study completion)

- Relationship between change in bone mineral density from Baseline in Study MBGS205 to Week 48 in Study MBGS206 and absolute levels of oestradiol and total testosterone at Week 48 in MBGS206
2. In subjects that were randomised to placebo in Study MBGS205 by dose group:
- Percentage change in hip bone mineral density measured by DEXA (g/cm^2) from Baseline in Study MBGS206 to Week 48
 - Percentage change in bone turnover markers (CTx1, osteocalcin, bone alkaline phosphatase, and P1NP) from Baseline in Study MBGS206 to Week 48
 - Change of oestradiol (absolute and percentage) from Baseline in Study MBGS206 to Week 48
 - Proportion of subjects with T-scores ≤ -2.5 at Week 48 of Study MBGS206
 - Proportion of subjects that overshoot testosterone (total testosterone above 1000 ng/dl [35 nmol/L] from first dose of study drug in Study MBGS206 until study completion)
 - Change in PSA from Baseline in Study MBGS206 to Week 48
 - Change in haematocrit from Baseline in Study MBGS206 to Week 48
 - Change in blood pressure (systolic and diastolic) Baseline in Study MBGS206 to Week 48

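### The 90-day limit on AE, SAE and AESI reporting ends before the Week 60 follow-up visit: nominally by one day for completers, and by about 22 to 29 days for men stopped at a fourth missed dose

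*Protocol*

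**What the plan says.** Three windows in the protocol share one closing rule.

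- **AEs (section 12.1.2):** after consent, a detrimental change "up to 90 days after the last administration of study drug should be considered an AE".
- **SAEs (section 12.1.8):** "SAE from the time of informed consent until the 90 days after last dose of study drug".
- **AESIs (section 12.1.8):** "AESI from the time of randomisation until 90 days after last dose of study drug".

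Other parts of the plan look further ahead.

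- Table 9-1 schedules AE assessment, laboratory tests including haematology and PSA, total testosterone, blood pressure and a limited physical examination at Week 60. Footnote 13 reads "AEs, SAEs, and AESIs collected from signature of informed consent" and gives no end date.
- Section 9.3.4 sends every man who stops the drug to Visit 8, 12 weeks after his EOT visit. For men who cannot attend, it keeps phone contact, with AE and AESI data still collected.
- The secondary safety endpoint (section 13.4.2.1) is "Treatment emerged AE, SAE, and AESI (from first dose of study drug in Study MBGS205 until study completion". Men switched from placebo have the same end point, counted from their first MBGS206 dose.
- SAP section 7.1.4.1 sets no upper time limit on TEAEs, and SAP section 8.7.4 summarises AEs for the follow-up period.

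**The concern.** The closing rule is tied to the last dose, whereas the final safety visit is tied to EOT. The longer the interval between last dose and EOT, the further the visit falls beyond the window. The protocol itself creates a group for whom that interval is long, because one criterion for mandatory discontinuation is "Subject missed 4 or more consecutive study drug dosing".

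A site that follows Table 9-1 would record an event that a site following sections 12.1.2 and 12.1.8 need not record. New-onset non-serious AEs, AESIs and unrelated SAEs in the last stretch before Visit 8 could then be captured at some sites and not at others, although the endpoint is meant to include them. AESIs established by a test or examination, such as haematocrit above 54% or oedema of Grade 3 or higher (section 12.1.7), are the plainest case, since they would ordinarily be dated to the visit at which they are first measured.

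**Working it through.** **Inputs**

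- First MBGS206 dose at Week 24: "starting with the first dose being taken at the baseline visit" (section 9.1.1).
- Number of doses: "The treatment period will consist of up to 24 weekly doses of BGS649" (section 9.1.1). Dose tolerance is ±1 day.
- Follow-up visit at Week 60, 12 weeks after Week 48/EOT (section 9.1.1), with a tolerance of ±2 days (Table 9-1).
- EOT visit within 7 days of discontinuation, and follow-up 12 weeks after EOT (section 9.3.4).

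**Check of the plan's own timeline.** 60 − 24 = 36 weeks, which matches the maximum duration in SAP section 3.3. Six dispensing visits (Weeks 24 to 44) × 4 weekly doses = 24 doses. Nothing is dispensed at Week 48, so the last planned dose is at Week 24 + 23 = Week 47.

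**Completers**

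- Last dose: 47 × 7 = day 329 of the combined schedule.
- Window closes: 329 + 90 = day 419.
- Follow-up visit: 60 × 7 = day 420.
- Visit minus last dose: 420 − 329 = 91 days, so the nominal gap is 91 − 90 = 1 day.
- With tolerances: 91 − 1 − 2 = 88 to 91 + 1 + 2 = 94 days. Of the 3 × 5 = 15 whole-day combinations, 9 exceed 90.
- If Week 60 is counted from an EOT visit that is itself ±2 days, the range is 86 to 96 days, and 44 of 75 combinations exceed 90.
- Share of the EOT-to-follow-up interval covered on the nominal schedule: (90 − 7) / (91 − 7) = 83/84 = 98.8%.

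**Men stopped for four missed doses** (assuming the stop is dated at the fourth missed dose)

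- Fourth missed dose: 4 × 7 = day 28 after the last dose taken.
- EOT visit: day 28 to 35.
- Follow-up visit: 28 + 84 = day 112 to 35 + 84 = day 119.
- Outside the window: 112 − 90 = 22 to 119 − 90 = 29 days.
- Share of the EOT-to-follow-up interval covered: (90 − 28)/84 = 62/84 = 74% down to (90 − 35)/84 = 55/84 = 65%.

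**Other early stoppers.** If the stop is decided 0 to 7 days after the last dose (an assumption) and EOT follows within 7 days, the visit falls between 84 and 7 + 7 + 84 = 98 days. Some of these visits are inside the window.

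**Provision beyond the window.** Section 12.1.2 asks investigators to notify SAEs that they learn of after the follow-up visit and that can reasonably be related to study drug. It does not reach non-serious AEs, non-serious AESIs or unrelated SAEs.

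**The case against.** The strongest reply is that little would be lost in practice, and much of it stands.

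- **Onset, not discovery.** A reader might infer that whatever is found at Week 60 is unreportable. The text does not say that. Section 12.1.8 speaks of events that occur during the study, and section 12.1.2 of changes in condition up to day 90. An event with earlier onset that comes to light at the visit is still covered.
- **Completers.** The gap is about one day, and the tolerances put many visits at or before day 90. The 9-in-15 count shows how many permitted combinations pass day 90. Reading it as 60% of visits needs all combinations to be equally likely, which no document supports, and it is not a share of events lost.
- **Collection.** A reader might infer that the endpoint is counted over a longer period than events are collected. That is not established: Table 9-1, footnote 13 and section 9.3.4 all support collection through Visit 8. The documents disagree with each other; they do not uniformly stop at day 90.
- **Analysis.** The SAP would not drop late events. Haematocrit, blood pressure and oedema grade at Week 60 are summarised as data whether or not an AE is filed (SAP sections 8.7.5.1, 8.7.6 and 8.7.7). Osteoporosis by DEXA is measured at EOT, so it is unaffected.
- **AESI start.** A reader might infer that AESI reporting has no start, or a late one, for men continuing active drug, because footnote 2 of Table 9-1 has only former placebo subjects randomised in MBGS206. Continuing men were randomised in MBGS205, so a literal reading opens their window earlier. For switchers, consent confirmation and allocation fall at the same visit. No lost event follows.

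What the reply does not remove is the contradiction in wording, or the 22 to 29 days before Visit 8 in missed-dose stoppers.

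**Conclusion.** The inconsistency is real and minor. Followed literally, the 90-day rule leaves out only events with onset after day 90. For on-schedule completers these are mainly findings first dated at the visit itself. For men stopped at a fourth missed dose they are new events in about the last 22 to 29 days before the visit, and the stretch lengthens if more doses are missed before the stop is declared.

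The documents give no expected number of such men, so the number of events at risk cannot be estimated. The figures assume nominal weekly dosing with all 24 doses taken by completers, and a stop dated at the fourth missed dose. I read study completion for a given man as Visit 8. Section 9.1.1 defines the end of the study as the last visit of the last subject, and that reading does not shorten the gap.

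**What to change.** In sections 12.1.2 and 12.1.8, end the AE, SAE and AESI windows at *the Follow-Up visit (Visit 8) or 90 days after the last dose, whichever is later*. This keeps the present 90-day minimum and brings collection into line with Table 9-1, section 9.3.4 and the endpoint.

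As a small reconciliation, start AESI reporting in section 12.1.8 at signature of the MBGS206 informed consent, as footnote 13 of Table 9-1 already has it.

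The cost is protocol and eCRF-guideline wording. No visit or procedure is added, and a few more late events may be recorded.
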